"A minimal clinically important difference (MCID) score for the WHODAS 2.0 has not yet been established. It is difficult to find studies with populations comparable to the present study in the literature. Based on clinical experience and the sparse available literature, a conservative minimal clinically important difference was taken to be five scale points on WHODAS 2.0 12-item version, and within-groups SD was taken to be 10 scale points. With a power level of 80% and alpha of 0.05, we estimate a sample size of each group of 64 and a total of 128. The completion rate in the preceding randomised trials at the CTP was two thirds, and we, therefore, set the expected drop-out rate to 35% for this study. The investigators increased the number of patients included to 128 × (1/ (100%-35%)) and, consequently, estimated a total sample size of 197 patients. Inclusion stops when approximately 197 patients are included in the trial. In the case that an MCID for WHODAS 2.0 is established during the time frame of the trial, this will be considered in the analyses. For the secondary outcome measures with a Cohen's d of 0.5, we have 80% power to detect a change of 0.21 on HTQ, 3.03 on HDRS, 3.77 on HARS, 0.25 on HSCL, 3.0 on SDS, 8.0 on WHO-5, 4.05 on GAF-F, and 2.85 on GAF-S."

In 2022, the Danish Health Authority assessed the MCID for the WHODAS 2.0 12-item and chose a standardised mean difference (SMD) of 0.3^2 . Based on this, we will revise the MCID from 5 scale points to 3 scale points to align with the Danish Health Authority when interpreting our findings.

7. Confidence intervals and p-values

Two-sided 95% confidence intervals will be reported for all estimated effects.

A two-sided p-value of <0.05 will be considered statistically significant for outcomes.

8. Analysis populations

Intention-to-treat (ITT) population

All randomised participants will be included in the ITT analysis, which will be conducted according to their assigned groups, regardless of their adherence to the intervention.

Per-protocol (PP) population

The PP analysis will include participants who fulfil completer criteria as per protocol. Completer criteria include attending five MD sessions, 10 psychologist sessions, and, additionally, two intersectoral collaborative meetings for the intervention group.

9. Outcome measures

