The primary analysis will compare the change in functioning scores (WHODAS 2.0) from pre- to posttreatment between the TAU and intervention group with adjustment for the corresponding baseline measures by ANCOVA/linear regression and with multiple imputations to handle missing data. The analysis will follow the ITT principle, including all randomised participants with available data.

Secondary and explorative analyses

Secondary outcomes will be analysed similarly using ANCOVA/linear regression.

11. Interim analyses

No interim analyses are performed.

12. Handling of missing data

The proportion and amount of missing data will be reported. Missing data will be addressed using multiple imputations, under the assumption that data is missing at random. Sensitivity analyses will be conducted to assess the robustness of the findings in relation to different missing data mechanisms (*see 14. Sensitivity analyses*).

13. Covariate adjustment

Analyses will be adjusted for the stratification variable and no other, complying with RCT analysis guidelines from the European Medicines Agency. For outcome variables, we will adjust for their corresponding baseline measure.

14. Sensitivity analyses

Sensitivity analyses will be conducted to assess the robustness of the primary results and will be reported as supplementary to the main analyses.

Baseline covariates found to be imbalanced between the intervention and TAU groups will be identified based on group comparisons and included as covariates in adjusted outcome analyses.

We will examine whether participants with missing post-treatment outcome data differ systematically from those with complete data by comparing baseline characteristics.

To explore the potential impact of missing data, outcomes will be calculated with all missing outcome data replaced with a value equalling the mean of the outcome variable ± 2 standard deviations.

We will conduct observed case analyses.

Additionally, we will conduct a PP analysis to evaluate the influence of adherence to the intervention. Results from the PP analysis will be compared with the ITT analysis to assess whether non-adherence may have affected the study outcomes.

15. Assumptions

To ensure the validity of the statistical models used in this study, the following assumptions will be tested:

- a) Normality of residuals
 Assumption: Model residuals should be approximately normally distributed.
 Control: Visual inspection using histograms and Q-Q plots of residuals.

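### SAP Section 14's only check beyond missing at random, the mean ± 2 SD fill, leaves sign by arm and source of mean and SD open, and shows no intermediate departures

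*SAP*

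**What the plan says.** Section 12 sets the main approach: "Missing data will be addressed using multiple imputations, under the assumption that data is missing at random". It then makes a promise and refers to Section 14 for it: "Sensitivity analyses will be conducted to assess the robustness of the findings in relation to different missing data mechanisms".

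Section 14 lists three items on missing data:

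- A look at whether participants without post-treatment data "differ systematically from those with complete data by comparing baseline characteristics".
- The fill, in which "outcomes will be calculated with all missing outcome data replaced with a value equalling the mean of the outcome variable ± 2 standard deviations".
- A single sentence: "We will conduct observed case analyses".

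The other two items in Section 14, adjustment for imbalanced baseline covariates and the per-protocol analysis, address different questions. All of these analyses "will be reported as supplementary to the main analyses".

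On the likely extent of the problem, Section 6 says "The completion rate in the preceding randomised trials at the CTP was two thirds", and the investigators therefore "set the expected drop-out rate to 35% for this study".

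**The concern.** The baseline comparison is descriptive and gives no effect estimate. The observed-case analysis does not model missingness that depends on the unseen outcome. Section 12's promise on mechanisms therefore rests on the one sentence about the fill.

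That sentence does not say whether the two arms get the same sign or opposite signs, or whether mean and SD are pooled or arm-specific. Reporting both a + run and a − run does not settle either point. Two analysts could follow the text and report quite different results.

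Whichever reading is taken, the fill applies one fixed displacement of 2 SD. A reader who doubts MAR wants to know how much worse the unobserved intervention participants would have to be before the conclusion changes. If a sizeable share of outcomes is missing, that is a central question for the primary result, and the planned checks do not report an answer.

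**Working it through.** **Inputs from the SAP.** Section 6: SD 10, planning difference 5, N = 197, drop-out 35%, revised MCID 3. Section 9: WHODAS 2.0 scored 0-48, lower is better. Section 3: 1:1 allocation.

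**Assumptions.** Missing share p of 10%, 20% or 35%, equal by arm unless stated; outcomes missing completely at random; pre-post correlation r from 0 to 0.7. Benefit is the TAU mean minus the intervention mean, so a positive value favours the intervention.

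**1. The plan's own figure.** 2 × (1.96 + 0.84)² × 10² / 5² = 62.7, so 63 per arm by the normal approximation. The t-test gives 63.77, so 64. Then 128 / 0.65 = 196.9, so 197. The sample size reproduces and is not in dispute.

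**2. Same sign, equal shares.** With a pooled mean, the same value is filled in both arms and cancels, so the reported benefit is (1 − p) × d. For d = 5 this is 0.65 × 5 = 3.25 at 35%, 4.0 at 20% and 4.5 at 10%, for + and for −. With arm-specific means the displacement cancels completely and 5.0 is reported.

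**3. Same sign, 40% missing in intervention and 30% in TAU.** Put the observed means at −5 (intervention) and 0 (TAU).

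- Pooled observed mean: −5 × 0.6/1.3 = −2.31.
- Pooled SD: √(100 + 25 × 0.6 × 0.7/1.3²) = 10.31.
- Fill value F: −2.31 ± 20.61, so 18.30 or −22.92.
- Reported benefit: 0.3F − (0.6 × (−5) + 0.4F) = 3 − 0.1F, so 1.2 or 5.3.
- With arm-specific means: 5 ∓ 0.1 × 20, so 3.0 or 7.0.

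The movement comes from the difference in missing shares and the chosen sign.

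**4. Opposite signs.** With arm-specific means the benefit is d ∓ 4 × 10 × p. With pooled values it is (1 − p)d ∓ 4p × 10.31, where 10.31 = √(100 + 25/4). For d = 5:

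| Missing per arm | Shift, 4 SD × p | Adverse run, arm / pooled | Favourable run, arm / pooled |
|---|---|---|---|
| 10% | 4 | 1.0 / 0.4 | 9.0 / 8.6 |
| 20% | 8 | −3.0 / −4.2 | 13.0 / 12.2 |
| 35% | 14 | −9.0 / −11.2 | 19.0 / 17.7 |

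The adverse run reverses a 5-point benefit at 20% and 35% missing, but not at 10%.

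**5. Where the conclusion would change.** Worsen the imputed intervention-arm values by δ. The estimate is d − pδ, with SE = 10 × √(1 − r²) × √(4/(197(1 − p))).

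- At p = 0.35 the SE is 1.77, 1.53 or 1.26 for r = 0, 0.5 or 0.7. Significance is lost at δ = (5 − 1.98 × SE)/0.35 = 4.3, 5.6 or 7.1 points.
- The estimate falls below the MCID at (5 − 3)/0.35 = 5.7 points.
- By the same formula, significance is lost at about 9 to 14 points with 20% missing and about 20 to 29 points with 10% missing.

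**6. Why the shifts must vary by arm.** With equal shares the estimate is d − p(δ_intervention − δ_TAU), so a common shift cancels. A shift of +5 in intervention and −5 in TAU gives 5 − 0.35 × 10 = 1.5.

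A simulation of the full method kept values within 0-48 (300 trials, 20 imputations, r = 0.5, 35% missing, assumed WHODAS mean 24 or 30). An intervention-arm shift of 20 gave −1.2 to −1.6, against 5 − 0.35 × 20 = −2.0 by formula, because the scale limits cut the shift short. A true 8-point benefit was still significant in 76-79% of trials at a shift of 10 and in 4-7% at 20, so a ±10 grid would usually miss that tipping point.

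**The case against.** The wording speaks of all missing data and of the mean of the variable, not of each group. It leans towards one pooled value with the same sign in both arms, run twice. Opposite signs are never mentioned. A reader might infer from the arithmetic that the check can turn a 5-point benefit into anything from an 11-point harm to a 19-point benefit. Those extremes need the less natural reading and 35% missing, so they are not a fair summary of the plan. The same holds for an inference that the fill reverses any plausible benefit: at 10% missing it does not reverse even a 5-point one, and significance is then lost only at or beyond a 2 SD shift.

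The 35% is also open to challenge. It comes from a completion rate, Section 8 defines completers by sessions attended, and people who stop treatment may still be assessed. The SAP states no expected share of missing outcomes.

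Further, a bounding analysis is a legitimate way to explore the impact of missing data, and the SAP promises no tipping point. A reader given the estimate, its confidence interval and the missing shares by arm could approximate one by hand.

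These objections limit the size and severity of the point. They do not remove it. The natural reading is the one that tests least between the arms, the open choices remain open, and an approximation left to the reader is not a pre-specified analysis.

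**Conclusion.** The point holds as a worthwhile improvement, not as a threat to the primary analysis. The fill is supplementary, no decision rule depends on it, and the primary estimate does not change.

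The gap in specification follows from the text alone. So does the absence of intermediate departures, since every reading uses a single 2 SD displacement. On the natural reading the check dilutes the effect or moves it with the difference in missing shares. On the opposite-sign reading it is an outer bound, and how severe it is depends on how much is missing.

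The sizes rest on SD 10, a 5-point benefit, the stated missing shares and, for loss of significance, r between 0 and 0.7. At 35% missing, the shifts that would alter the conclusion (about 4 to 7 points for significance, 5.7 for the MCID) lie well inside 2 SD, where the plan looks at nothing. At 10% missing this argument is much weaker, but the unstated sign and source still need fixing.

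**What to change.** In Section 14, add a delta-adjusted multiple-imputation (tipping-point) analysis for WHODAS 2.0:

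- Impute under MAR with treatment arm in the imputation model.
- Add shifts to the imputed values, varied independently by arm, over a pre-stated grid, for example 0 to ±20 points.
- Pool by Rubin's rules.
- Report the shift at which the 95% CI first includes 0 and the shift at which the estimate falls below 3 points, or state that neither is reached within the grid.
- If values are kept within 0-48, also report the mean shift actually applied.

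Keep the ± 2 SD fill as an outer bound. State the sign by arm, whether mean and SD are pooled or arm-specific, and how out-of-range values are handled. With SD 10, both fill values lie within 0-48 only if the mean is between 20 and 28.

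The cost is a few lines of SAP text, a short loop over the imputed data in Stata and one supplementary table. No new data are needed.
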